### **3.4** Early Withdrawal of Subjects

### 3.4.1 When and How to Withdraw Subjects

- Recurrent or Progressive Disease: Subjects who have clinical or radiologic evidence of recurrent disease will undergo an evaluation to document the nature of the abnormality. If recurrent or progressive cancer is diagnosed, the subject will be considered off study at that time.
- PI Decision: Subjects may be withdrawn at any time during the study if the PI believes it is in the subject's best interest. In this event, the reasons for withdrawal will be documented.
- Subject Participation: Refusal to continue treatment, follow-up, comply with the protocol or withdrawal of consent. In this event, the reasons for withdrawal will be documented.
- Adverse Event (including intercurrent illness, unacceptable toxicity).

Once the subject has discontinued treatment, the primary reason for discontinuing treatment must be clearly documented in the subject's records and on the CRF. The investigator will assess each subject for response at the time of withdrawal.

Every effort will be made to follow all subjects off study for toxicity and survival unless patient withdraws consent. If subjects withdraw from the study at any time, we will ask for his/her written permission to continue to access medical records for overall survival. Acute toxicities will be assessed for 90 days from the first date of treatment. Survival will be followed for a minimum of 5 years.

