#### 7.1.2.2 Secondary Endpoints

Late toxicity is defined as any grade 3 or higher toxicity, considered probably or definitely related to radiation, observed later than 90 days from completion of therapy excluding cranial nerve palsies or nerve root symptoms as these may be due to the tumor itself or prior surgery. Late toxicities will be graded according to the CTCAE version 4.0. The time frame for late toxicity is open-ended and late toxicities have been known to occur a year or more after therapy. Follow-up for late toxicity will cease when a patient experiences disease progression, since 2nd line therapies may then be initiated.

Progression-free and overall survival are defined as the time from start of radiotherapy to first documented progression (local or distant event for PFS), death due to any cause or last patient contact alive. The local control rate (i.e., local progression only) may also be evaluated.

Fatigue will be scored by the Brief Fatigue Inventory (BFI), a validated instrument, which will be evaluated at the following time points: Pre-radiation, during treatment, at the inspection visit, and at approximately 3, 6, 9, 12 months post-radiation and then every 6 months for years 2 and 3, and yearly for year 4 and 5. It is expected that BFI score will increase (as fatigue worsens) in the first 6-12 months post-radiation and then the BFI score will decrease (as fatigue improves) at 12-24 months post-radiation.

Neurocognitive function will be assessed by the FACT-BR, which will be evaluated at preradiation, during treatment, at 3, 6, 9, 12 months post-radiation and then every 6 months.

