#### 7.2.4 Statistical Analyses.

Analyses of acute and late toxicity and fatigue will be completed within 1 year of completion of accrual. Time-to-event outcomes and long term longitudinal measurements of fatigue and neurocognitive function will be analyzed 2-3 years after completion of accrual. Descriptive analyses and subset analyses are likely. The purpose of these subset analyses is hypothesis generation. Subgroup analyses will likely describe time-to-event outcomes by histology (e.g., chordoma or chondrosarcoma) and extent of surgery (e.g., biopsy only, partial debulking, and maximal debulking). They will produce estimates of clinical outcomes, to aid in the design of future clinical trials.

Acute and Late Toxicity. All acute and late toxicities will be graded by CTCAE Version 4.0 and tabulated. Toxicity rates and 95% confidence intervals will be calculated. The maximum half-width of the 95% confidence interval is  $\pm 14\%$  based on 50 patients.

Time-to-Event Outcomes. Trials of chordomas and chondrosarcomas which combine proton with photon, have demonstrated 5-year progression-free survival rates (i.e., free of local failure) of 60-80%. We do not expect the 5-year PFS rate to be much different with protons. Progression-free and overall survival and time to local failure, will be estimated by the Kaplan-Meier method. Median and 5-year estimates and 95% confidence intervals will be calculated.

Fatigue (Brief Fatigue Inventory, BFI) & Neurocognitive function (FACT-Br) will be summarized by mean and standard deviation calculated and plotted over time. We will examine the plots for the expected worsening of function in the 6-12 months post-radiation and gradual improvement from 12-24 months. Pre- and post-treatment comparisons at a primary time point (e.g., at 24 months post-radiation when function should have recovered) will be evaluated by Student's paired t-test or nonparametric Wilcoxon signed ranks test. A general strategy to assess trends over time in longitudinal data is to employ linear mixed effects models, which can account for the impact of covariates such as anti-seizure medication and baseline performance status. The BFI can also be categorized as mild (1-3), moderate (4-6) and severe (7-10). The rates of patients in the severe category will be estimated at each time point. Of primary interest are the rates at 12 and 24 months post-treatment.

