#### Radiation Toxicities

Radiation side effects are typically divided into those that occur acutely and those that occur later. Common acute radiation side effects include fatigue, skin irritation or erythema, alopecia, nausea, vomiting and diarrhea. Typically, these side effects can be controlled with medication. Late side effects that are unlikely to occur would include radiation necrosis of the brain, brainstem injury, vascular effects (e.g. stroke), severe dementia, blindness, deafness, paralysis, and skin necrosis. Another rare but serious late side effect is the development of second tumors. It is hoped that proton radiation will substantially reduce both acute and late side effects by reducing the amount of normal tissue that is irradiated.

Acute radiation effects, through post treatment day 90 of treatment, and late radiation effects will be evaluated using the CTCAE 4.0..

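### Late-toxicity follow-up stops at progression in Section 7.1.2.2 but continues off study in Section 3.4.1, and no analysis method handles the follow-up that is cut short

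*Combined protocol and SAP*

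**What the plan says.** Two sections of the combined protocol and SAP govern toxicity follow-up in a patient whose disease progresses.

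- Section 7.1.2.2 defines late toxicity as Grade 3 or higher, probably or definitely related to radiation, and seen more than 90 days after therapy ends. It describes the period at risk in these words: "The time frame for late toxicity is open-ended and late toxicities have been known to occur a year or more after therapy". It then sets a stop: "Follow-up for late toxicity will cease when a patient experiences disease progression". The reason given is that second-line treatment may begin at that point. Section 7.2.2 applies the same endpoints to Phase II.
- Section 3.4.1 says of progression: "If recurrent or progressive cancer is diagnosed, the subject will be considered off study at that time". It goes on: "Every effort will be made to follow all subjects off study for toxicity and survival unless patient withdraws consent". Withdrawal of consent is the only exception. The one time limit on toxicity there concerns acute events: "Acute toxicities will be assessed for 90 days from the first date of treatment". Survival is to be followed for at least 5 years.

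Section 7.2.4 plans toxicity rates with 95% confidence intervals, quotes a maximum half-width of 14 points on 50 patients, and places the toxicity analysis within 1 year of the end of accrual. On progression it says that earlier trials combining protons and photons "have demonstrated 5-year progression-free survival rates (i.e., free of local failure) of 60-80" percent, and adds: "We do not expect the 5-year PFS rate to be much different with protons".

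**The concern.** A patient who progresses is off study, so Section 3.4.1 calls for continued toxicity follow-up and Section 7.1.2.2 calls for it to end. Staff cannot do both. The choice decides whether late injury after progression is recorded at all.

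Section 7.2.1 makes characterizing toxicity a purpose of Phase II. Section 8.1 lists late effects such as brain necrosis, brainstem injury and blindness, and says: "Another rare but serious late side effect is the development of second tumors". Nothing suggests that these risks end when the tumor progresses. Other reporting routes do not fill the gap. Section 8.3.2 ends SAE reporting to the DSMC six months after the last subject is treated, and Section 8.3.1 asks for IRB reports of adverse events only when they are both unexpected and related.

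The analysis compounds the problem. If follow-up stops at progression and the rate is a simple proportion of all treated patients, those who progressed count as free of late toxicity for years in which nobody looked, and the rate is biased downward.

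**Working it through.** **The plan's own figure.** The maximum 95% half-width with n = 50 is 1.96 × √(0.5 × 0.5/50) = 13.9 points, which agrees with the stated 14.

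**Inputs from the documents.** 5-year PFS of 60-80% (7.2.4); 50 patients (7.2.1); enrolment over 4 years (7.3); toxicity analysis within 1 year of the end of accrual (7.2.4); treatment usually completed within 9 weeks (4.6); late toxicity counted from 90 days after completion (7.1.2.2). The late window therefore opens at t0 = (63 + 90)/365.25 = 0.42 years.

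**Assumptions.** Exponential PFS; uniform accrual; a constant late-toxicity hazard from t0, independent of progression; every PFS event treated as a progression that ends late-toxicity follow-up. The documents give no late-toxicity rate for this trial, so a true 5-year risk of 10% is used for illustration.

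**1. Patients with an event by 5 years.** 50 × (1 − 0.80) = 10 and 50 × (1 − 0.60) = 20.

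**2. Hazard.** h = −ln(PFS)/5, which is 0.0446 per year at 80% and 0.1022 at 60%.

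**3. Person-time lost to 5 years.**
- Clock from the start of treatment: observed time is (1 − PFS)/h, or 0.2/0.0446 = 4.48 and 0.4/0.1022 = 3.92 of 5 years. The loss is 10% and 22%.
- Clock from t0: observed time is (e^(−h·t0) − PFS)/h, or 4.07 and 3.51 of 4.58 years. The loss is 11% and 23%.

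**4. Position at the planned analysis.** Follow-up F is uniform from 1 to 5 years.
- Share with a PFS event: 1 − (e^(−h) − e^(−5h))/(4h) = 12% and 26%.
- Mean late window: 3 − 0.42 = 2.58 years. The observed part, (e^(−h·t0) − e^(−hF))/h averaged over F, is 2.37 and 2.12 years. The loss is 8% and 18%.

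**5. Effect on a crude 5-year rate.** With a true risk of 10%, λ = −ln(0.9)/4.58 = 0.0230 per year. The counted rate is λ/(λ + h) × e^(−h·t0) × (1 − e^(−(λ + h) × 4.58)).
- PFS 80%: 0.340 × 0.981 × 0.266 = 8.9%.
- PFS 60%: 0.184 × 0.958 × 0.436 = 7.7%.

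The shortfall is 1.1 to 2.3 points, or about 0.6 to 1.2 patients in 50. If all late toxicity began in years 2 to 5, the counted rate would be about 8.6% and 7.0%.

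**6. Comparison with precision.** At a rate of 10% with n = 50, the half-width is 1.96 × √(0.1 × 0.9/50) = 8.3 points.

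**The case against.** The stop rule looks deliberate. Section 7.1.2.2 gives its reason, and the plan is alert to tumor-caused symptoms: it excludes cranial nerve palsies and nerve root symptoms on that ground. Attribution becomes harder at progression itself, not only when second-line therapy starts. Section 3.4.1 is a general best-efforts statement whose stated durations are 90 days for acute toxicity and 5 years for survival, so one could read its mention of toxicity as acute only. The bias is also small beside the sampling error.

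Much of this stands. Progression is a defensible cut-off for the main estimate. Moving it to the start of second-line therapy would be a debatable choice, and the documents give no figure for the interval between the two. The size argument is right as well.

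Two things survive. The follow-up sentence in Section 3.4.1 is not limited to acute toxicity, so the sections still conflict. Difficulty of attribution is a reason to report later events apart; it is not a reason to leave them unrecorded, since the definition already requires a probable or definite relation to radiation.

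A reader might infer that 20-40% of late injury would be missed. The documents do not support that. The figure is the share of patients with a PFS event by 5 years, and toxicity before progression still counts. The cited PFS is also glossed as freedom from local failure, whereas the trial's own definition includes distant events and deaths, and a patient who dies without progressing loses nothing through this rule.

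**Conclusion.** The conflict is real and in current text, and the sections must be reconciled. The analysis gap is also real: Section 7.2.4 does not say how follow-up cut short by progression enters the late-toxicity rate.

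The consequence is a modest downward bias. About 10-23% of late-toxicity person-time is lost to 5 years, and about 8-18% at the planned analysis, when some 12-26% of patients would have had a PFS event. An assumed true risk of 10% would be counted as about 7.7-8.9%. These figures rest on exponential PFS, uniform accrual, toxicity independent of progression, and the cited 60-80% applying here.

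The bias is conditional. A reader might take the 50 patients in Section 7.2.4 as the late-toxicity denominator, but that number appears there only in a maximum half-width; the denominator is not defined. The downward bias follows if patients who progress stay in a crude proportion.

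**What to change.** 1. Amend Section 7.1.2.2 to agree with Section 3.4.1: radiation-related Grade 3 or higher late toxicity continues to be recorded after progression, within the existing off-study follow-up. Record the dates of progression and of any second-line therapy.
2. In Section 7.2.4, estimate the late-toxicity rate by a time-to-event (cumulative incidence) method with follow-up censored at progression, not as a crude proportion of 50. Death without progression is a competing event. Progression should not be made a competing event as well, because that would return the shortfall shown above.
3. Tabulate post-progression events separately, before and after second-line therapy, with attribution.

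The cost is a few sentences, two dates on the case report form, and some work to collect toxicity off study, for which the protocol gives no visit schedule. Attribution is harder after progression and ascertainment will be less complete, which is why those events stay out of the main estimate. Censoring assumes that patients who progress would otherwise have had the same later toxicity risk as those who do not; the separate table gives a rough check on that.

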### 6.1 Post-treatment Evaluation and Follow-up

All subjects will be evaluated weekly during the course of the proton therapy, at the inspection visit (approximately 90 days from treatment start) and approximately every three months from the last dose of treatment either by the treating radiation oncologist or a referring physician for two years, and approximately every 6 months for year 3 and then yearly for years 4 and 5. Patients will be treated and followed for 90 days from the start of radiation treatment to determine feasibility and safety (acute toxicity) for the initial phase of the study before moving to the second phase of the study.

Each follow-up examination will consist of interval history and physical examination, including a neurologic evaluation and toxicity assessment. A Brief Fatigue Inventory and FACT-Br will also be obtained. Assessment of the disease by MRI will be performed at intervals of 3 months for 2 years and then every 6 months for year 3 and annually for years 4 and 5.

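### PFS is censored at last contact alive, so patients who leave imaging follow-up without documented progression count as progression-free after their last scan

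*Combined protocol and SAP*

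**What the plan says.** Section 7.1.2.2 gives PFS and overall survival a single definition: time from the start of radiotherapy to "first documented progression (local or distant event for PFS), death due to any cause or last patient contact alive". The only element specific to PFS is the progression event. The end date for patients without an event is shared. Section 7.2.2 carries these endpoints into phase II.

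No other section supplies a censoring date for PFS. Section 6.1.2 states one for overall survival only. Section 7.2.4 names the Kaplan-Meier method for PFS, overall survival and time to local failure, and promises median and 5-year estimates with 95% confidence intervals.

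On follow-up after leaving the study, section 3.4.1 says: "Every effort will be made to follow all subjects off study for toxicity and survival unless patient withdraws consent". For subjects who withdraw, "we will ask for his/her written permission to continue to access medical records for overall survival". It adds: "Survival will be followed for a minimum of 5 years". Disease imaging belongs to the on-study schedule in section 6.1: "Assessment of the disease by MRI will be performed at intervals of 3 months for 2 years", then every 6 months in year 3 and yearly in years 4 and 5.

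**The concern.** Knowing that a patient is alive is enough to keep that patient at risk for death. It is not enough to keep the patient at risk for documented progression, which needs a disease assessment. Section 3.4.1 opens several exits that do not involve progression: PI decision, adverse event, and "Refusal to continue treatment, follow-up, comply with the protocol or withdrawal of consent". After such an exit the plan names toxicity and survival follow-up but no scans. Under the shared definition the PFS clock still runs to the last contact, so the unscanned time enters the Kaplan-Meier estimate as progression-free time.

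The disease makes this more than a formality. Section 1.1 describes chordoma as slow-growing and mainly a local problem, and gives 5-year survival of about 80% for chordoma and 100% for chondrosarcoma. Section 7.2.4 expects 5-year PFS of 60-80%. Many patients therefore outlive progression, and death, the other PFS event, will often not reveal a missed progression within 5 years. Section 7.2.4 sets the PFS result beside that 60-80% range and intends the subgroup time-to-event estimates to inform the design of later trials. An upward bias would carry into both uses.

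**Working it through.** **The plan's own figure.** There is none to reproduce. The documents give no sample size, event count or power for PFS.

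**Who is affected.** Section 3.4.1 says of one exit: "If recurrent or progressive cancer is diagnosed, the subject will be considered off study at that time". Those patients already have a PFS event. The affected group is patients who stop imaging without documented progression and remain known to be alive.

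**Inputs.**
- 5-year freedom from progression S of 0.6, 0.7 or 0.8, from the range in section 7.2.4.
- MRI schedule from section 6.1.
- Share d who stop imaging but stay in vital-status contact: not in the documents; 10%, 20% and 30% assumed.
- Also assumed: stopping time uniform over years 0-5 and unrelated to progression, constant progression hazard, complete vital-status contact, and no clinical detection of progression after the last scan.

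**Step 1, by hand, ignoring deaths.** If everyone is in contact to 5 years, the Kaplan-Meier estimate is the share never seen to progress. For a patient who stops at a uniform time, the chance of not having progressed by then is (1 - S)/(-ln S). Hence

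bias = d x [(1 - S)/(-ln S) - S].

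- S = 0.6: 0.4/0.511 = 0.783; 0.783 - 0.6 = 0.183. For d = 10%, 20%, 30%: 1.8, 3.7, 5.5 points.
- S = 0.7: 0.3/0.357 = 0.841; 0.841 - 0.7 = 0.141. Result: 1.4, 2.8, 4.2 points.
- S = 0.8: 0.2/0.223 = 0.896; 0.896 - 0.8 = 0.096. Result: 1.0, 1.9, 2.9 points.

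**Step 2, with the MRI schedule, ignoring deaths.** Progression is found only at a scheduled scan, so the last scan comes somewhat before the stopping time and the bias is slightly larger. Simulation with 200,000 patients per scenario gave:

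| S | d = 0 | d = 10% | d = 20% | d = 30% |
|---|---|---|---|---|
| 0.6 | 0.0 | +2.1 | +4.2 | +6.3 |
| 0.7 | 0.0 | +1.6 | +3.2 | +4.8 |
| 0.8 | 0.0 | +1.1 | +2.2 | +3.3 |

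**Step 3, with deaths.** Assumed death hazards are 0.01 per year before progression and 0.10 per year after it. Some missed progressions now end in a death that counts as an event, so the bias shrinks. Across S = 0.8 to 0.6 it is about 0.9 to 1.7 points for d = 10%, 1.8 to 3.4 for 20% and 2.6 to 5.0 for 30%.

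**Step 4, the alternative rule.** In the same model, censoring survivors at the last scan while still counting every death as an event gives a bias of about -0.3 to -1.3 points. Among patients who have stopped imaging, those who die stay in the risk set until an event while those who live are removed early, so censoring depends on outcome. When deaths after imaging has stopped are also censored at the last disease assessment, the bias is within 0.2 points.

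**The case against.** The strongest counter-argument is that few patients may be affected, and that those few are not wholly out of sight.

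- Off-study patients are followed for toxicity as well as survival. Section 7.1.2.2 ends late-toxicity follow-up at progression, which presumes that progression status is known. Some progressions would surface this way.
- Records access limited to survival concerns only those who withdraw and give permission.
- Section 3.4.1 asks for a response assessment at withdrawal.
- For patients who stay on schedule, visits and scans coincide, so the two censoring dates hardly differ.
- PFS has no test, stopping rule or go/no-go decision. With 50 patients and complete follow-up, the 95% half-width for a 5-year rate is 1.96 x sqrt(0.6 x 0.4/50) = 13.6 points at 60%, and 1.96 x sqrt(0.8 x 0.2/50) = 11.1 points at 80%. The illustrated bias is well inside that.

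All of this limits the size and stands to that extent. It does not repair the rule. Toxicity contact is not scheduled imaging, an assessment at withdrawal says nothing about later time, and a confidence interval does not show a bias that runs in one direction.

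A reader might infer that everyone off study is affected. The documents do not support that, since the progression exit is itself a PFS event. A reader might also infer that moving censoring to the last scan is enough. Step 4 shows that it is not, unless deaths after imaging has stopped are dealt with too.

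**Conclusion.** The PFS censoring rule is wrong as written. It is a stated rule with the wrong end date, not merely a missing detail. Whenever patients leave imaging follow-up without documented progression and remain in contact, it biases 5-year PFS upward under the assumptions used here. As an illustration the overstatement is about 1-2, 2-3 and 2.5-5 points for 10%, 20% and 30% of such patients, and nil if there are none.

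Those sizes rest on the assumed dropout shares, uniform stopping times, full vital-status contact, no clinical detection, the two death hazards, and stopping unrelated to progression. A reader might take them as the bias this trial will have. The documents give no rate of stopping imaging, and the screening allowances in section 7.3 (18 for 12 and 50 for 38) are not that rate. Nor does the point touch the feasibility or toxicity conclusions. It concerns the reported estimates of a secondary, descriptive endpoint.

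**What to change.** Split the definition in section 7.1.2.2:

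- **Overall survival:** unchanged, censored at last contact alive.
- **PFS and time to local failure:** patients without an event are censored at the last disease assessment showing no progression.
- **Deaths, for PFS:** a death while the patient is still under scheduled imaging is an event. A death after imaging follow-up has stopped is censored at the last disease assessment. A sensitivity analysis counts all deaths as events.

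The cost is a few sentences. The scans are already scheduled, so no visits or patients are added. The PFS estimate may come out slightly lower. The new rule also assumes that stopping imaging is unrelated to progression, and the report should say so.

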#### List of Abbreviations

AE: Adverse Event

ANOVA: Analysis of Variance BFI: Brief Fatigue Inventory BPI: Brief Pain Inventory CNS: Central Nervous System

CR: Complete Response CRF: Case Report Form

CT: Computerized Axial Tomography

CTCAE: Common Terminology Criteria (CTC) for Adverse Events

CTV: Clinical Target Volume

DSMB: Data and Safety Monitoring Board DSMC: Data and Safety Monitoring Committee

EBRT: External Beam Radiotherapy

ECG: Electrocardiogram

EORTC: European Organization for Research and Treatment of Cancer

EQ-5D: European Quality of Life Index

FACT-BR: Functional Assessment of Cancer Therapy-Brain FACT-G: Functional Assessment of Cancer Therapy-General

FDA: Food and Drug Administration

FDG: Fludeoxyglucose GTV: Gross Tumor Volume

Gy: Gray

HIPAA: Health Insurance Portability and Accountability Act

IUD: Intra-Uterine Device LET: Linear Energy Transfer

MRI: Magnetic Resonance Imaging NCI: National Cancer Institute OAR: Organ at Risk Volume

OER: Oxygen Enhancement Ratio PAR: Planning Organ at Risk Volume

PD: Progressive Disease

PBSTV: Pencil Beam Scanning Target Volume

PET: Positron Emission Tomography

PFS: Progression Free Survival PHI: Protected Health Information

PI: Principal Investigator PR: Partial Response

RC-REVIEW: Range Compensator Review Volume

RBE: Relative Biologic Effectiveness

RTOG: Radiation Therapy Oncology Group

SAE: Serious Adverse Event

SD: Stable Disease

SOBP: Spread Out Bragg Peak SOP: Standard Operating Procedure SWOG: Southwest Oncology Group WBC: White Blood Cell Count

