#### **Secondary Objectives**

To assess acute side effects from irradiation using proton beam therapy for the treatment of chordomas or chondrosarcomas.

To assess late complications from irradiation using proton beam therapy for the treatment of chordomas or chondrosarcomas.

To compare the dose distribution to tumor and surrounding normal structures using DVH's (Dose Volume Histograms) generated from the proton plan used to treat the patient and the photon plan generated for comparison purposes.

To monitor the rates of local control as well as overall and disease specific survival using proton radiotherapy.

Version: 04/04/2014

To evaluate the time to progression and progression free survival of chordomas or chondrosarcomas treated with protons.

To evaluate the effect of proton beam radiation on neurocognitive outcome in patients with chordomas or chondrosarcomas.

To evaluate the quality of life (e.g., fatigue) in patients treated for chordomas or chondrosarcomas.

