# **6.0 Study Procedures**

Patients will complete the Brief Fatigue Inventory and Fact Br which is specific to patients with CNS tumors. Fatigue and neurocognitive testing for these patients will continue for 3 years post radiation.

	Eligibility/ Pre- treatment	Weekly during treatment	1.1	O Follow-Up  X Months (approximat ely from completion of treatment) 3,6,9,12,15, 18, 21, 24 (approx.)	Months 30, 36 (approximatel y from completion of treatment)	1
Tests and						
Observations						
History and PE	X			X	X	X
ECOG Score	X		X	X	X	
CT/MRI	X			X	X	X

CXR	$X^3$					
Pathology	X					
Pregnancy Test	$X^1$					
Toxicity	X	X	X	X	X	X
Assessment						
Tumor	$X^2$			$X^2$	$X^2$	$X^2$
Measurement						
BFI (fatigue)	X	X	X	X	X	X
Fact Br (neurocog)	X	X	X	X	X	X

 $X^{I} A \text{ pregnancy test will be required for females of child bearing potential within 5 days of tx)}$ 

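### The neurocognitive endpoint rests only on FACT-Br, a patient-completed functional questionnaire, so it can describe self-reported function but cannot establish a change in neurocognitive function

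*Combined protocol and SAP*

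**What the plan says.** Section 2 lists two separate secondary objectives. One is "To evaluate the effect of proton beam radiation on neurocognitive outcome in patients with chordomas or chondrosarcomas". The other is "To evaluate the quality of life (e.g., fatigue) in patients treated for chordomas or chondrosarcomas".

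Section 7.1.2.2 turns the first into an endpoint with a single instrument: neurocognitive function "will be assessed by the FACT-BR, which will be evaluated at preradiation" and at subsequent visits. The List of Abbreviations gives the instrument's full name: "FACT-BR: Functional Assessment of Cancer Therapy-Brain". Section 6.0 says who fills it in: "Patients will complete the Brief Fatigue Inventory and Fact Br which is specific to patients with CNS tumors". The next sentence there reads "Fatigue and neurocognitive testing for these patients will continue for 3 years post radiation", and the only row of the schedule that mentions cognition begins "Fact Br (neurocog".

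For follow-up visits, Section 6.1 lists history and physical examination, "including a neurologic evaluation and toxicity assessment", plus the BFI and FACT-Br. For analysis, Section 7.1.4 gives FACT-Br descriptive summaries and scatter plots. Section 7.2.4 gives it means and standard deviations over time, a paired comparison with baseline (24 months is the example), and mixed models as a general strategy. Neither section says which FACT-Br score is used or picks out any part of the form as cognitive.

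**The concern.** The objective names one construct and the instrument, as the protocol itself describes it, names another. A questionnaire on which patients report their own functioning may be worth having, but it is not a test of cognition, and calling its administration testing does not make it one.

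The practical risk lies in the report. The endpoint definition, the schedule and both analysis sections carry the FACT-Br result under a neurocognitive label. A pre-to-post difference would therefore be written up as an effect on neurocognitive function, whatever led patients to rate themselves differently. The plan does not say how a change that merely accompanies fatigue would be told apart from a change in cognition. Section 7.2.4 intends its subset estimates to help in designing later trials, so a mislabelled result could be carried forward.

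**Working it through.** This is a question of what is measured, so the check is to follow the endpoint through the documents.

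1. **Objective (Section 2).** Neurocognitive outcome is listed apart from quality of life and fatigue. The protocol treats it as a distinct question.
2. **Instrument (Sections 7.1.2.2 and 6.0).** FACT-Br is the only measure assigned to it.
3. **Nature of the instrument (List of Abbreviations and Section 6.0).** It is named a functional assessment and is completed by the patient.
4. **Any other cognitive measure (Sections 6.0, 6.1, 7.1.4 and 7.2.4).** None is listed. Section 6.0 speaks of neurocognitive testing, but no test other than FACT-Br is named. The neurologic evaluation and CTCAE 4.0 toxicity grading take place, but neither is assigned to this endpoint.
5. **Expected course.** The relevant text compares as follows.

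| Section | Instrument covered | Expectation |
|---|---|---|
| 7.1.2.2 | BFI only | fatigue worsens over the first 6-12 months, improves at 12-24 months |
| 7.1.2.2 | FACT-Br | none stated |
| 7.1.4 | BFI only | same course, to be looked for in the plots |
| 7.1.4 | FACT-Br | none stated |
| 7.2.4 | BFI and FACT-Br together | same course, to be looked for in the plots |

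Between the feasibility and phase II sections, an expectation stated for fatigue becomes one for FACT-Br as well, with no separate reason given. The plan thus expects its neurocognitive score to move on the fatigue timetable. The two covariates that Section 7.2.4 gives as examples for the mixed models are anti-seizure medication and baseline performance status; fatigue is not one of them.

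6. **Plan's own figures.** There is none for FACT-Br: no effect size, standard deviation, significance level or power. The only power statement, in Section 7.3, concerns severe fatigue (33% against a null of 50%, n = 50, one-sided 5%). It reproduces: SE under the null = √(0.5 × 0.5/50) = 0.0707; SE under the alternative = √(0.33 × 0.67/50) = 0.0665; (0.17 − 1.645 × 0.0707)/0.0665 = 0.807, giving 79.0% against the stated 79%. It has no bearing on this point. A larger sample would not cure a mismatch between construct and instrument either.

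Steps 1 to 5 are enough: the construct in the objective is never measured by performance, and the only measure that carries its name is self-reported function.

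**The case against.** The strongest reply is that little hangs on this. The endpoint is secondary, the trial has one arm, and the analysis is mainly descriptive. Section 7.2.1 gives the phase II purpose as toxicity, fatigue and progression-free survival, without mentioning cognition. FACT-Br is named beside the neurocognitive label in Sections 7.1.2.2, 7.1.4 and 7.2.4, so a careful reader can see what was measured. The BFI shares the same columns of the schedule, so fatigue can be inspected alongside. Follow-up visits also include a neurologic evaluation and toxicity grading, which might pick up gross cognitive events. All of this stands, and it is why the point is minor. It does not remove the mismatch, because none of it changes the heading under which the result would be reported.

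The reply also limits how far the point can go. Four stronger statements are tempting, and the documents support none of them.

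- *A quality-of-life change would be reported as a cognitive effect.* The documents never call FACT-Br a quality-of-life scale. Their abbreviation list uses that description for EQ-5D and calls FACT-Br a functional assessment. Nor do they say that the quality-of-life objective is served by the BFI alone; Section 2 mentions fatigue only as an example.
- *A real cognitive decline would be diluted in a stable total, with a calculable loss of power.* The documents give no items, domains or scoring and do not say that a total is analysed. Any power figure would only restate the assumptions put into it.
- *Cognition is a stated benefit sought from protons.* Section 7.2.1 expects less fatigue and toxicity. Section 7.2.4 names neurocognitive impairment as a known effect of photons but anticipates a reduction only in severe fatigue. Section 8.1 expresses a general hope of fewer side effects.
- *The form has no cognitive content.* The documents do not show its content. It may ask about cognition, and the answers would still be self-report.

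**Conclusion.** The concern holds as a mismatch between objective and instrument. As planned, a change in self-reported function, including one that follows the course of fatigue, would be presented as a change in neurocognitive function, and FACT-Br alone cannot establish that. The data can still describe how patients rate their own function over time; what is unsupported is the cognitive conclusion.

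This is a minor point on one secondary endpoint, and it carries no number. It rests on the protocol's own description of FACT-Br and on the absence of any other assigned cognitive measure. It needs no assumption about the form's items or scoring.

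**What to change.** In Sections 2, 6.0, 7.1.2.2, 7.1.4 and 7.2.4:

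- rename the FACT-Br endpoint *patient-reported function (FACT-Br)*, including the schedule label and the reference to neurocognitive testing in Section 6.0;
- reword the neurocognitive objective to match;
- state that no conclusion about neurocognitive function will be drawn from the overall FACT-Br score.

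If the form contains cognition-related items and they are captured individually, summarise them separately as *patient-reported cognitive complaints*. The documents do not show whether either condition is met, so this step is conditional.

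The cost is a set of wording changes and, where possible, one extra summary from forms already being collected. No new test or visit is needed. The downside is a narrower claim.
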